### **Status of the study as of 15-Oct-2015:**

Eighteen (18) patients have been randomized onto this study; the proposed changes will have no impact on the interpretation of the data with the exception of the definition of the evaluable (MITT) population which clarifies that patients must all have a baseline DXA (identical to ITT) and at least one post-baseline DXA.

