## 4.2 Exclusion criteria

Patients fulfilling any of the following criteria are not eligible for inclusion in this study. No additional exclusions may be applied by the investigator, in order to ensure that the study population will be representative of all eligible patients.

1. History of primary bone disease (osteogenesis imperfecta, idiopathic juvenile osteoporosis, rickets/osteomalacia).
2. Any prior use of bisphosphonates, or high dose sodium fluoride (i.e. dental use is permitted).

3. Any medical condition that might interfere with the evaluation of LS-BMD, such as severe scoliosis or spinal fusion. Patients with less than 3 evaluable vertebrae by DXA evaluation in the region of interest L1-L4, as confirmed by the central imaging laboratory, will not be considered eligible for this study.
4. As per investigator's judgment, patient is anticipated to have bone surgery within subsequent year.
5. Hypocalcemia and hypophosphatemia: any value (age-matched) below the normal range at screening.
6. Serum 25-hydroxy vitamin D concentrations of < 20 ng/mL or < 50 nmol/L at screening.
7. Renal impairment defined as an estimated glomerular filtration rate (GFR) < 60 mL/min/1.73 m^2 at screening based on the Schwartz formula at screening
8. A serum creatinine increase between Visit 1 and Visit 2 greater than 0.5 mg/dL (44.2 µmol/L).
9. Uncontrolled symptoms of cardiac failure or arrhythmia.
10. History of hyperparathyroidism or hyperthyroidism within 1 year prior to screening.
11. History of hypothyroidism unless on a stable treatment regimen for > 6 months, with at least one documented normal TSH and FT4 levels during this 6 month period.
12. History of sarcoidosis.
13. Diagnosis of active uveitis (symptomatic or asymptomatic) at the time of enrollment in the study.
14. History of hypersensitivity to any of the study drugs or its excipients or to drugs of similar chemical classes

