### **9.1.2 Modified Intention-to-treat (MITT) population**

The MITT population will consist of all patients in the ITT population who have an evaluable baseline assessment for the endpoint of interest.

Patients will be included in the MITT population for the analysis of the primary efficacy endpoint (change in lumbar spine Z-score at Month 12 relative to baseline) if their DXA assessments includes baseline and at least one post-baseline LS-BMD score.

According to the ITT principle, patients will be analyzed with respect to the treatment to which they were randomized.

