- If the event date occurs after the first infusion date (inclusive), then the study day is defined as the date of the event minus the first infusion date plus 1.

Visit schedule

Summaries by visit will be based on the visits collected on the CRF and no visit window will be applied. Only scheduled visits will be included in the summary, unless specified otherwise.

Subjects and treatments

The following analysis sets will be defined:

- Intention-to-treat (ITT) population

- Modified Intention-to-treat (MITT) population
- Per-protocol (PP) population
- Safety population

Intention-to-treat (ITT) population

The ITT population will consist of all randomized patients. Following the ITT principle, patients will be analyzed according to the treatment they are assigned at randomization. Disposition, protocol deviation, demographics, baseline disease characteristics, medical history, and disease-related background information will be based on ITT population.

Modified Intention-to-treat (MITT) population

The MITT population will consist of all randomized patients who have both baseline and at least one post-baseline LS-BMD Z-score. All efficacy analyses will be based on MITT population including primary efficacy analysis.

Safety population

The Safety population will consist of all patients who have been exposed to at least one infusion of study drug. Patients will be analyzed according to the treatment actually taken. All safety analyses will be based on Safety population.

Per-protocol (PP) population

The PP population will include all patients in the MITT population who do not have any protocol deviations that could confound the interpretation of analyses conducted on the MITT population. Prior to unblinding, the Clinical Trial Team and Trial Statistician will identify the major protocol deviations that will exclude patients from the PP population. Primary efficacy endpoint will also be analyzed in the PP population.

Important protocol deviations for exclusion from analysis sets are specified in Appendix section “PD and non-PD criteria leading to exclusion from analysis sets” and others will be identified by the clinical team before the final database lock.

Pooling of centers

Centers will be pooled into four regions based on the similarity of clinical practice for randomization and analysis purpose. The regions are as follows:

- North America region
 - United States
 - Canada
- EMEA America region
 - Belgium
 - Finland
 - Germany
 - Hungary
 - Italy

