Furthermore, summarizations by ATC class will be provided with regard to a group of specified concomitant medications/significant non-drug therapies, which include osteoporosis-related medications, nutritional supplements, and glucocorticoids. The summary table will be sorted by ATC class in decreasing order of frequency in the zoledronic acid group.

Missing date convention

If the medication start and end dates are recorded in the CRFs, medications that start on or prior to the first infusion in study and end on or after the first infusion in the study including ongoing at end of the study were included in both prior to and after start of study drug administration in the study, respectively.

Partial medication start dates will be imputed as follows:

- Only day is missing: the partial start date will be imputed using 15MONYYYY if the month and year indicate that the medication started prior to the first infusion of study medication or 01MONYYYY if the month and year indicate that the medication started on or after the first infusion of study medication.
- Both day and month are missing: the partial start date will be imputed using 01JULYYYY if the year indicates that the medication started prior to the first infusion of study or 01JANYYYYY if the year indicates that the medication started on or after the first infusion of study medication.

Partial medication end dates will be imputed as follows:

- Only day is missing: the partial end date will be imputed using the last date of the month.
- Both day and month are missing: the partial end date will be imputed as December 31 if the end year is prior to the year of first infusion of study drug or one day after the

last study infusion date if end year is equal to or after the year of first infusion of study drug.

Efficacy evaluation

Analyses of all efficacy endpoints will be performed on the MITT population. Confirmation of the result for the primary efficacy endpoint will be conducted using the PP population without imputation for missing data. All efficacy measurements will be presented in listings.

Analysis for the primary objective

The primary objective is to demonstrate that zoledronic acid administered every 6 months at 0.05 mg/kg (max 5 mg) is superior to placebo for the change in lumbar spine (LS) bone mineral density (BMD) Z-score at Month 12 relative to baseline.

Variable

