Appendix

PD and non-PD criteria leading to exclusion from analysis sets

Analysis Set	PD ID (that causes subjects to be excluded)	Non-PD criteria (that causes subjects to be excluded)
ITT		Not randomized
MITT		Not in ITT; No baseline BMD Z-score; No post-baseline Z-score
SAF		No study drug taken
PPS	All inclusion and exclusion criteria; S01; S02; S03; M01	Not in MITT

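### The SAP requires a post-baseline LS-BMD Z-score for every efficacy endpoint, but protocol 9.1.2 requires it only for the primary one, so some observed secondary outcomes, chiefly Month 3 pain, leave the between-group analysis

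*SAP*

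**What the plan says.** **SAP.** The section on the Modified Intention-to-treat population states: "The MITT population will consist of all randomized patients who have both baseline and at least one post-baseline LS-BMD Z-score". It then applies that set throughout: "All efficacy analyses will be based on MITT population including primary efficacy analysis". The Efficacy evaluation section repeats the scope: "Analyses of all efficacy endpoints will be performed on the MITT population". The section on secondary objectives again names MITT, without imputation. The Appendix table of exclusion criteria lists the reasons for leaving MITT as "Not in ITT; No baseline BMD Z-score; No post-baseline Z-score", so a missing post-baseline Z-score is enough on its own.

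**Protocol.** Section 9.1.2 opens with an endpoint-specific rule: "The MITT population will consist of all patients in the ITT population who have an evaluable baseline assessment for the endpoint of interest". The LS-BMD requirement follows in a separate sentence with its own scope: "Patients will be included in the MITT population for the analysis of the primary efficacy endpoint", provided there is a baseline and at least one post-baseline LS-BMD score. Section 9.5.1 then uses MITT for the secondary efficacy variables.

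**A third wording.** The Amendment 5 note on study status describes the evaluable (MITT) population in DXA terms: "patients must all have a baseline DXA (identical to ITT) and at least one post-baseline DXA". It does not limit this to the primary endpoint.

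**The concern.** For the secondary endpoints, the SAP conditions entry to the analysis on a measurement that most of them do not use. Pain comes from the FPS-R, turnover markers from blood, and fracture, morphometry and cortical width from X-rays. Total body BMC comes from a different DXA region. A child can have a baseline and a follow-up value for one of these and still be left out for lack of a follow-up lumbar spine Z-score.

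This is an exclusion made after randomisation. It is avoidable, because the outcome was observed and the protocol's own definition would keep the child. The SAP gives no reason for the change and plans no alternative set for these endpoints: the per-protocol set is nested within MITT and is used for the primary endpoint only. At stake are some precision in secondary comparisons and, where leaving early is related to how the child is doing, the comparability of the arms at the early pain visit.

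**Working it through.** **1. Which half of the SAP condition matters.** Inclusion criterion 4 already requires a centrally confirmed screening LS-BMD Z-score, so the baseline half should remove almost nobody. The post-baseline half is the one with effect.

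**2. Schedule (protocol Table 6-1; sections 5.6.2 and 6).** Post-baseline DXA is due at Month 6, at Month 12 and at the discontinuation or withdrawal visit. One Z-score from any of these is enough for MITT.

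| Secondary endpoint | Post-baseline collection | Child left out although observed |
|---|---|---|
| Pain (FPS-R) | Months 3, 6, 9, 12 (3 and 9 by telephone) | Month 3 value present; leaves before the Month 6 DXA with no discontinuation scan |
| Serum markers | Months 6, 12 | Blood drawn, but no Z-score at any DXA visit |
| New vertebral fracture, morphometry, cortical width | Month 12 or discontinuation | Readable film, but no Z-score at any DXA visit |
| Total body BMC | Months 6, 12 | Usable total body scan, but no lumbar spine Z-score at any DXA visit |
| Lumbar spine BMC, Month 6 LS-BMD Z-score | Months 6, 12; Month 6 | Essentially none: same lumbar scan |

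Only Month 3 pain is measured before any scheduled post-baseline DXA. Month 9 pain is affected only if the Month 6 scan was missed and no later scan was made. The other rows need a child to attend a DXA visit and give the other measurement but no usable lumbar Z-score.

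**3. The plan's own sample size.** Inputs from protocol 9.8 and the SAP: difference 0.63, SD 0.93, two-sided 0.05, power 85%, 1:1 allocation.

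- Normal approximation: n per arm = 2 × (1.960 + 1.036)² × 0.93² / 0.63² = 39.1, so 40 per arm.
- Noncentral t: power is 84.9% at 40 per arm and 85.8% at 41, so 41 per arm, or 82, matches the plan.
- Dropout: 82 / 0.90 = 91.1, which rounds up to 92, or 46 per arm.

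The figure reproduces, and nothing in this point changes it.

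**4. Outer bound on children affected.** 92 − 82 = 10, and 10 / 92 = 10.9%. This would be reached for an endpoint only if every planned dropout had that endpoint observed and no post-baseline Z-score. The documents do not give the true number, so the range is 0 to about 10.

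**5. Precision.** With m children left out, the standard error grows by √(92 / (92 − m)):

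- m = 2: 1.011
- m = 5: 1.028
- m = 10: 1.059

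For pain, the responder rates below are assumptions, since the documents give none. Going from 46 to 41 per arm (m = 10, split evenly), power changes as follows:

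- 30% vs 50%: 49.9% to 45.5%
- 40% vs 60%: 48.3% to 44.0%
- 30% vs 60%: 83.6% to 79.0%

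So even at the outer bound the loss is between 4 and 5 percentage points.

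**The case against.** **The protocol is not uniform.** The Amendment 5 status note reads much as the SAP does, and the SAP authors may have followed it. That explains the mismatch but does not remove it. Section 9.1.2 is the operative definition, and it confines the post-baseline LS-BMD condition to the primary endpoint. The note needs reconciling too.

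**Most endpoints share visits with DXA.** This stands. Discontinuing children are asked for the full final-visit assessments, including DXA, and one Z-score at any time suffices. A reader might infer that fracture, markers, morphometry and cortical width are affected as much as pain; the schedule does not support that.

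**Fracture bias.** A reader might also infer that a new L1-L4 fracture makes the scan unevaluable, so that exclusion depends on the fracture outcome. The documents do not say so. The rule on "Patients with less than 3 evaluable vertebrae by DXA evaluation in the region of interest L1-L4" is an entry criterion (protocol 4.2), and nothing states that a follow-up scan failing it is set to missing. Children with vertebral fractures at entry are eligible and must still have an evaluable spine. A fracture after an evaluable Month 6 scan cannot remove a child from MITT.

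**Dropout is not the number affected.** This also stands. A child who leaves with no final visit has no film either, and is absent from the fracture analysis under both definitions. Any worked shift in the fracture p-value would rest on invented event counts.

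**The data are not discarded.** Correct: the SAP lists all efficacy measurements, tabulates the analysis populations by arm and lists ITT patients excluded from efficacy. The affected endpoints are secondary and carry no multiplicity-controlled claim. The SAP as written still omits these children from the treatment comparison.

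**Conclusion.** The point holds as a contradiction between SAP and protocol on the analysis set for secondary efficacy endpoints. Its demonstrable effect is on Month 3 FPS-R, in children who leave before the Month 6 DXA without a discontinuation scan. For total body BMC, markers and the X-ray endpoints the effect is probably small, and for fracture it may be close to nil.

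The size is 0 to about 10 of 92 children for any one endpoint. This rests on the assumption that the number without a post-baseline Z-score does not exceed the planned dropout allowance; the upper end would need all of those children to have the secondary outcome observed. The corresponding standard error inflation is at most about 6%. The direction and size of any bias cannot be derived from the documents. Both documents agree on the post-baseline LS-BMD condition for the primary endpoint, so the primary analysis and its sample size are untouched.

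**What to change.** In the SAP, define the set for each secondary efficacy endpoint as all randomised children with an evaluable baseline for that endpoint and an observed value at the visit analysed, grouped as randomised. Keep the post-baseline LS-BMD condition for the LS-BMD Z-score endpoints only. Amend the two general statements of scope and the MITT row of the Appendix exclusion table to match, and reconcile the protocol's amendment status note with section 9.1.2.

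If the sponsor prefers a single set, the SAP should give the reason and add, for each non-BMD endpoint, an analysis of all randomised children with that endpoint observed.

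The cost is SAP wording and endpoint-level inclusion flags. No new data are needed and the primary analysis does not change. The drawback is that the number analysed will differ slightly between tables, so each table should state its own denominator.

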### **3 Investigational plan**

#### **3.1 Study design**

This will be an international, multicenter, randomized, double-blind, placebo controlled efficacy and safety study recruiting osteoporotic children and adolescents receiving glucocorticoid therapy within the 12 months preceding screening who manifest a LS-BMD Z-score of -0.5 or worse plus evidence of low impact/fragility fracture.

At the baseline visit (Visit 2), patients whose eligibility is confirmed will be randomized to one of two treatment groups. Patients may be hospitalized at the discretion of the investigator for observation following the first study drug infusion. Ionized calcium will be assessed before the first study drug infusion only. Patients will receive the second study drug infusion at the Month 6 visit. Safety and efficacy will be assessed at 6 and 12 months, with additional telephone visits to assess adverse events [REDACTED] and concomitant medication at 3 and 9 months. Renal safety utilizing the Schwartz calculation for GFR will be assessed at screening, and 10 days after the i.v. infusion of study drug 6 and 12 months.

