## **5.6 Study Completion and Discontinuation**

### **5.6.1 Study completion and post-study treatment**

A patient will be considered to have completed the study when the patient has completed all the assessments in the last visit planned in the protocol (Visit 8, Month 12).

Continuing care should be provided by investigator and/or referring physician based on patient availability for follow-up. This care may include:

- Enrollment in the extension study: Patients who complete the 12 month study will be offered a 12 month extension study where all patients will receive zoledronic acid CZOL446H2337E1.
- Alternative therapy may be prescribed at the discretion of the treating physician at Month 12.

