### 9.3.2 Concomitant therapy

Concomitant medications will be coded using the WHO Drug Reference List that employs the Anatomical Therapeutic Chemical classification system. Summary tables will be provided that present the number and percent of patients receiving those medications by preferred term and treatment after start of study drug administration. The medications will be sorted in decreasing order of frequency with respect to usage in the zoledronic acid group.

Descriptive summary statistics (mean, median, standard deviation, minimum, maximum) will be provided for the dose and duration of use of glucocorticoids by treatment group at baseline and during the 12-month double-blind period. Descriptive summary statistics (mean, median, standard deviation, minimum, maximum) will also be provided for the duration of exposure to glucocorticoid treatment between randomization and the end of double-blind treatment. The number and percentage of patients receiving different types of glucocorticoid therapy will be presented by preferred term and treatment group.

Usage of calcium and vitamin D will be summarized by treatment group with respect to the forms of calcium and vitamin D taken.

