 - Systemic lupus erythematosus (SLE)
 - Juvenile dermatomyositis
 - Scleroderma (generalized or localized)
 - Overlap syndromes (including mixed connective tissue disease)
 - Sjogren's syndrome
 - Systemic vasculitis
 - Giant cell (temporal) arteritis
 - Takayasu's arteritis
 - Polyarteritis nodosa
 - Wegener's granulomatosis
 - Churg-Strauss syndrome
 - Microscopic polyangiitis
 - Essential cryoglobulinemic vasculitis
 - Cutaneous leukocytoclastic angiitis
 - Behcet's disease
 - Other vasculitis
- Inflammatory bowel disease:
 - Crohn's disease
 - Ulcerative colitis
- Duchenne muscular dystrophy
- Nephrotic syndrome
- Other

Frequency counts will be provided for the derived disease types and sub-types by treatment group as well as the total in a table.

Relevant medical history and current medical conditions

Relevant medical history/current medical conditions will be summarized by primary system organ class, preferred term and treatment group with frequencies and percentages displayed. A patient with multiple occurrences of a medical condition for a preferred term or system organ class is counted only once in each specific category. A corresponding listing will also be provided.

Extent of exposure

A summary table will be provided for the exposure to study medication, including number of patients with any infusion, duration for 1st infusion, duration for 2nd infusion, volume for 1st infusion, and volume for 2nd infusion.

Prior/concomitant medications and significant non-drug therapies

The number and percentage of patients receiving prior and concomitant medications and significant non-drug therapies will be summarized by treatment group and preferred term according to the WHO Drug Reference List employing the Anatomical Therapeutic Chemical (ATC) classification system. Prior medications are defined as those ending prior to the first infusion of study drug; medications ending on or after the first infusion of study drug are concomitant medications. Prior medications will be presented separately from concomitant medications. The summary table will first be sorted by ATC class alphabetically and then by preferred term in decreasing order of frequency with respect to usage in the zoledronic acid group.

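### A medication end date with only a year, in the first-infusion year or later, is set to the day after the last infusion, so glucocorticoid courses can end in the wrong year or before they start

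*SAP*

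**What the plan says.** For an end date with day and month missing, the SAP (Prior/concomitant medications, Missing date convention) has two branches:

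- End year before the first-infusion year: "the partial end date will be imputed as December 31 if the end year is prior to the year of first infusion of study drug".
- Any later end year: one day after the "last study infusion date if end year is equal to or after the year of first infusion of study drug".

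A start date with only a year, on or after first infusion, becomes "01JANYYYYY if the year indicates that the medication started on or after the first infusion of study medication".

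On timing, Protocol 3.1 says "Patients will receive the second study drug infusion at the Month 6 visit", and Protocol 5.6.1 places study completion at Visit 8, Month 12. The last planned infusion is therefore mid-study.

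Protocol 9.3.2 promises descriptive statistics by treatment group for "the duration of exposure to glucocorticoid treatment between randomization and the end of double-blind treatment". The SAP names glucocorticoids as a specified medication group but describes only summaries by ATC class for them.

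On classification, the SAP's main text says "Prior medications are defined as those ending prior to the first infusion of study drug"; medication ending on or after first infusion is concomitant, and the two are tabulated separately. The first paragraph of the missing-date convention says that medications spanning the first infusion "were included in both prior to and after start of study drug administration in the study".

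**The concern.** An imputed date should agree with the part of the date that is known. Here a known end year can be overridden in either direction, and a course begun in the second half of the study can be given an end before its start. The SAP has safeguards for adverse events: a year-only end date goes to 31 December, and a start date imputed after a completed end date is reset to that end date. It states no order check for medications, and the 31 December rule covers only the earlier end years.

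At stake is the table that lets a reader compare glucocorticoid exposure between arms, in a trial of glucocorticoid-treated children with a bone-density endpoint. A patient who stops after one infusion stays in the study and concomitant treatments are still collected (Protocol 5.6.2). The imputed end is then Day 2. If stopping differs by arm, so does the error.

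The classification conflict is a separate matter. It arises even with complete dates and decides whether a steroid ongoing at baseline also appears in the prior-medication table.

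**Working it through.** The plan gives no figure to reproduce here, so I applied the rule literally.

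**Inputs.** Last infusion on Day 180 (two infusions, Protocol Table 6-1) or Day 1 (one infusion); follow-up to Day 365. Imputed end = last infusion + 1 day, which is Day 181 or Day 2.

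**Examples (two infusions; calendar dates are illustrative)**

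| First infusion | Last infusion | Recorded | Imputed end | Result |
|---|---|---|---|---|
| 2 Mar 2015 | 28 Aug 2015 | end 2014 | 31 Dec 2014 | year kept |
| 2 Mar 2015 | 28 Aug 2015 | end 2016 | 29 Aug 2015 | wrong year, too early |
| 2 Mar 2015 | 28 Aug 2015 | start 2016 (set to 1 Jan), end 2016 | 29 Aug 2015 | duration −125 days |
| 2 Mar 2015 | 28 Aug 2015 | start 12 Oct 2015, end 2015 | 29 Aug 2015 | duration −44 days |
| 1 Oct 2015 | 28 Mar 2016 | end 2015 | 29 Mar 2016 | wrong year, too late |

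In the last row the course ended by 31 December 2015 at the latest, which is Day 92 (31 + 30 + 31). The imputed end is Day 181, so exposure is overstated by at least 181 − 92 = 89 days.

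**Share of end days put in the wrong year.** Assume first infusion is equally likely on each day d = 0, …, 364 of a 365-day year, and the true end equally likely on each of the 365 study days. That gives 365 × 365 = 133,225 combinations. For a given d, 365 − d end days fall in the first-infusion year and d in the next.

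- Two infusions: the imputed end is d + 180.
  - For d ≤ 184 it stays in the first year, so the d next-year end days are wrong: 0 + 1 + … + 184 = 17,020.
  - For d ≥ 185 it moves to the next year, so the 365 − d first-year end days are wrong: 1 + … + 180 = 16,290.
  - Total 33,310 / 133,225 = 25.0%.
- One infusion: the imputed end is d + 1.
  - For d ≤ 363, 0 + 1 + … + 363 = 66,066 end days are wrong; for d = 364, one is wrong.
  - Total 66,067 / 133,225 = 49.6%.

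**Courses that would end before they start.** These are courses starting after the imputed end: 365 − 181 = 184 of 365 start days with two infusions, and 365 − 2 = 363 of 365 with one. The same differences are the largest possible loss of exposure, in days, if the window runs to Month 12.

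**Prior/concomitant split.** Last infusion + 1 day is always after first infusion. So is 31 December of a year at or after the first-infusion year (or on the same day, at the extreme), capped at end of study or last contact. Both rules class the record as concomitant, so the split is unchanged. A course that really ended earlier in the first-infusion year, before first infusion, is classed as concomitant under either rule.

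**Classification conflict.** Take a steroid started before first infusion and stopped after it, with complete dates. Under the SAP's main text it is concomitant only. Under the missing-date paragraph it counts in both periods. The prior-medication tables differ.

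**The case against.** The strongest reply is that the rule serves the use the SAP gives it. The SAP uses medication dates to separate prior from concomitant and then counts patients, and that split does not change. This stands for the SAP's own tables. It does not cover the duration summary in Protocol 9.3.2, for which no other date convention is given, although neither document says outright that these imputed dates feed it.

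A second reply concerns the exposure window. Protocol 9.3.2 refers to the end of double-blind treatment, and Protocol 5.6.2 treats planned study drug as finishing at Visit 5, Month 6. On that reading an imputed end on Day 181 cuts nothing off. But Protocol 9.3.2 also speaks of a 12-month double-blind period, so the window is ambiguous. The 89-day overstatement in the last example remains even if the window closes at Month 6.

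Third, such records should be uncommon on study: medication is reviewed at every visit (Table 6-1), and Protocol 6.3 calls for intake dates for glucocorticoids. That is fair. The frequency is unknown.

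On the classification conflict, Protocol 9.3.2 separately promises glucocorticoid use at baseline, so ongoing steroids would not vanish from the report. That limits the harm but does not settle which prior-medication table is intended.

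**Conclusion.** The point holds, within limits. For year-only end dates in the first-infusion year or later, the rule can contradict the recorded year and can give negative durations. The two classification rules are also incompatible for medication spanning the first infusion. Both are wrong as written and minor.

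The size is about 25% of end days in the wrong year with two infusions and 49.6% with one. It rests on evenly spread infusion and end dates and applies only to records missing both day and month.

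Three stronger readings are not supported:

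- A reader might infer that every recorded year is ignored. Years before the first-infusion year are handled correctly.
- A reader might take these percentages as shares of patients. They are shares of hypothetical dates among affected records.
- A reader might infer a bias in the efficacy result. Glucocorticoid dose and duration are in no efficacy model; the primary ANCOVA uses treatment, pooled centers, underlying condition and baseline Z-score.

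**What to change.** 1. For an end date with day and month missing, impute 31 December of the recorded end year, capped at the end-of-study or last contact date, and never earlier than the start date. In the examples (Day 365 for the first patient is 29 February 2016):
   - end year 2016 with first infusion 2 March 2015 becomes 29 February 2016;
   - the course started 12 October 2015 ends on 31 December 2015;
   - end year 2015 with first infusion 1 October 2015 becomes 31 December 2015.
2. Keep one classification: ended before first infusion is prior, everything else is concomitant. Remove the conflicting sentence and show glucocorticoids ongoing at baseline in a separate row.

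The cost is about two sentences in the SAP and minor programming. There is a small downside: 31 December gives the longest exposure compatible with the recorded year, so it leans upward. It does keep the date in the recorded year unless the follow-up cap applies, and never before the start.
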